Statistical methods:	
The Clopper-Pearson 95% confidence interval (CI) of the incidence of post-dose levels of ALT or AST that meet the criteria for being considered a safety concern will be calculated for each dosage group. Similarly, the Clopper-Pearson 95% CI of the incidence of gastrointestinal (GI) distress reported by patients during the study will also be calculated. Other AEs will be summarized by using frequency tables. The incidence of abnormal data for safety measures will be presented for each dosage group. The continuous and discrete variables for safety data will be summarized with descriptive statistics (mean, median, standard deviation, minimum, and maximum) and frequency tables, respectively, at each assessment. For each dosage group, frequency tables will be used to summarize the response to each question of the questionnaire on treatment acceptability between Ferriprox IR vs. deferiprone DR. Based on the responses to the question on overall preference for one formulation or the other, a one-sample proportion test will be used to test if the overall preference for deferiprone DR is greater than 0.5 for each dosage group.
	
Version and date of the protocol:	Version 1.0, 10 OCT 2018	

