### **2.2 Secondary Objectives**

- To evaluate the tolerability of deferiprone DR tablets in two different dosage groups in patients with systemic iron overload
- To evaluate the acceptability to patients of deferiprone DR

The endpoints for the secondary objectives provided in [Section 9.1.2](#).

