### **3.2 Rationale for Study Design**

*Study population:* To date, four Phase I trials have been or are currently being conducted to assess the safety, tolerability, and pharmacokinetics of deferiprone delayed release tablets in healthy volunteers. This study will be the first to look at the DR formulation in the population for which it is intended. It is possible that the rates of adverse events that were seen in healthy subjects would occur at different rates in patients, due to the different action of an iron chelator in iron-overloaded vs. non-iron-loaded recipients.

*Dosages:* Patients with systemic iron overload are usually prescribed deferiprone at a dosage ranging from 75 mg/kg/day to 100 mg/kg/day. Dosages within both the upper half and the lower half of this range will be investigated, to determine if there is a dose effect on the adverse events that were seen in healthy subjects (due to tailoring of dosages to individual patient needs and to rounding, most potential subjects will not be on a dosage of Ferriprox that is exactly 75 mg/kg/day or exactly 100 mg/kg/day). In all cases, the total daily dosage of deferiprone DR will be made to match that of Ferriprox IR as closely as possible. Since dosages will be rounded to the nearest 500 mg and body weights of participants will differ, some variability is unavoidable.

*Safety Precautions:* The findings from the first 5 participants to be enrolled in either dosage group will be assessed before enrollment can continue. Details are provided in [Section 3.1.1](#). As a further precaution, alert events have been defined that will mandate extra monitoring or termination from the study in any patient in whom they are observed. Information on alert events is provided in [Section 4.5.1](#).

*Endpoints:* The endpoints are safety and acceptability. No endpoints for efficacy have been included, as bioequivalence of deferiprone DR tablets to Ferriprox IR tablets over a 24-hour period has already been demonstrated.

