#### 9.1.2 Secondary Endpoints

Secondary endpoints are as follows:

- The assessment of tolerability will be based on the incidence of gastrointestinal (GI) distress reported by patients during the study.
- The assessment of acceptability will be based on the number of patients who indicate that they prefer the DR formulation over Ferriprox IR after considering their preference with respect to scheduling, ease of administration, and tolerability.

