#### **9.4.1.3 Analysis of Safety**

The Clopper-Pearson 95% confidence interval (CI) of the incidence of post-dose levels of ALT or AST that meet the criterion for being considered a safety concern will be calculated for each dosage group. Similarly, the Clopper-Pearson 95% CI of the incidence of GI distress reported by patients during the study will also be calculated. Other AEs will be summarized by using frequency tables. The incidence of abnormal data for safety measures will be presented for each dosage group.

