#### **9.4.1.4 Analysis of Acceptability**

For each dosage group, frequency tables will be used to summarize the response to each question of the questionnaire in [Appendix 1](#) on treatment acceptability between Ferriprox IR vs. deferiprone DR. Based on the response to the question on overall preference for one

formulation or the other (Question #4), a one-sample proportion test will be used to test if the overall preference of deferiprone DR is greater than 0.5 for each dosage group.

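### Cheap improvement (minor, secondary endpoint): the plan analyses preference for DR only within each dosage group of 15; add one prespecified exact analysis in all patients beside the group results

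*Combined protocol and SAP*

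**What the plan says.** The secondary objective on acceptability is "To evaluate the acceptability to patients of deferiprone DR" (section 2.2). It names no dosage groups. The tolerability objective in the same list does: "To evaluate the tolerability of deferiprone DR tablets in two different dosage groups in patients with systemic iron overload". The acceptability endpoint in section 9.1.2 is the "number of patients who indicate that they prefer the DR formulation over Ferriprox IR", again without a split.

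The analysis in section 9.4.1.4 is by group throughout: "For each dosage group, frequency tables will be used to summarize the response to each question of the questionnaire". The test of Question 4 is described in the same way: "a one-sample proportion test will be used to test if the overall preference of deferiprone DR is greater than 0.5 for each dosage group". The synopsis agrees: "a one-sample proportion test will be used to test if the overall preference for deferiprone DR is greater than 0.5 for each dosage group". Question 4 in Appendix 1 has two answers, DR or Ferriprox, so a binomial analysis fits.

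Section 4.1 plans 15 patients per group, 30 in all. Section 9.2 says that no formal power calculation can be performed. The null value (0.5) and the direction of the test are stated; alpha and the choice between an exact and an approximate test are not. For the other binary endpoints section 9.4.1.3 names an exact method, for example "the Clopper-Pearson 95% CI of the incidence of GI distress reported by patients during the study will also be calculated".

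**The concern.** The objective asks one question about patients in general. The planned analysis answers it twice, in 15 patients each time, and has no line for the 30 together. If one group test succeeds and the other does not, the plan does not say what follows for the objective as written.

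Each group test alone is also weak against a moderate preference. With 11 of 15 preferring DR in both groups, each exact test gives p = 0.059, while the same 22 of 30 taken together gives p = 0.008. A pooled analysis chosen only after such a result, in an open-label study, would be open to challenge; one written down beforehand would not. At stake is how clearly one secondary endpoint can be reported.

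**Working it through.** The plan states no power, alpha or expected preference for this test, so it has no figure to reproduce.

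**Inputs.** From the documents: 15 patients per group and 30 in total (4.1); null value 0.5 and alternative above 0.5 (9.4.1.4). Assumed: exact binomial test, one-sided alpha 0.025 (which corresponds to a two-sided 95% interval), all patients answering, and true preferences between 0.50 and 0.80.

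**Cut-offs.** The cut-off is the smallest k with P(X ≥ k | n, 0.5) ≤ 0.025.
- n = 15: P(X ≥ 11) = 0.0592 and P(X ≥ 12) = 0.0176, so 12/15 is needed (size 1.8%).
- n = 30: P(X ≥ 20) = 0.0494 and P(X ≥ 21) = 0.0214, so 21/30 is needed (size 2.1%).
- The 95% Clopper-Pearson interval agrees with the test: 20/30 gives 47.2% to 82.7%, which includes 50%; 21/30 gives 50.6% to 85.3%, which does not.

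**Power.** One group's test has power q(p) = P(X ≥ 12 | 15, p): q(0.50) = 0.0176, q(0.60) = 0.0905, q(0.65) = 0.1727, q(0.70) = 0.2969, q(0.75) = 0.4613, q(0.80) = 0.6482. The plan runs two such tests, so a second comparator is the chance that at least one succeeds, 1 − (1 − q₁)(1 − q₂). For example, at 0.70 in both groups this is 1 − 0.7031² = 0.506. The pooled power is P(X₁ + X₂ ≥ 21), where X₁ and X₂ are independent binomial counts from 15 patients each.

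| True preference in the two groups | Pooled | Each group's test | At least one group test |
|---|---|---|---|
| 0.50 / 0.50 (false positive) | 2.1% | 1.8% / 1.8% | 3.5% |
| 0.70 / 0.70 | 58.9% | 29.7% / 29.7% | 50.6% |
| 0.75 / 0.75 | 80.3% | 46.1% / 46.1% | 71.0% |
| 0.75 / 0.65 | 58.9% | 46.1% / 17.3% | 55.4% |
| 0.70 / 0.60 | 35.7% | 29.7% / 9.1% | 36.1% |
| 0.80 / 0.60 | 59.0% | 64.8% / 9.1% | 68.0% |
| 0.80 / 0.50 | 34.8% | 64.8% / 1.8% | 65.4% |

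**Other alpha.** At one-sided 0.05 the exact group cut-off stays at 12/15, so the group columns do not change. The pooled cut-off falls to 20/30 (size 4.9%), with power 73.0% at 0.70 and 89.4% at 0.75.

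**The case against.** The strongest reply is that the by-group analysis is deliberate. Section 9.4.1.4 and the synopsis agree with each other, the design has two dosage groups, and section 9.2 promises no power. All of that stands, and it is why this is an improvement rather than a defect. The documents give no by-dosage reason for analysing preference, but one can be supplied. Section 3.2 studies both dosage ranges "to determine if there is a dose effect on the adverse events that were seen in healthy subjects", and Question 4 comes after a question on side effects and asks patients to weigh it. Preference could therefore differ by dosage, so the group results must stay.

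A reader might infer that pooling roughly doubles the power. That holds only against a single group's test. Against at least one success in the two planned tests, the gain at equal preference is 58.9 − 50.6 = 8.3 points at 0.70 and 80.3 − 71.0 = 9.3 points at 0.75. It disappears at 0.70/0.60 and turns into a loss at 0.80/0.60. The at-least-one reading does carry a higher false-positive chance, 3.5% against 2.1%.

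The all-patient total could also be had by adding the two group tables. That is true of the count, but no interval or test for it is planned. The example of 11/15 in both groups depends on the exact form: an uncorrected z-test gives p = 0.035 and would pass at one-sided 0.05.

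A reader might also infer that every withdrawal means a lost answer, because withdrawn patients are not replaced (4.5.3). The documents do not support this. Sections 3.1 and 5.1 and Table 5.1 place the questionnaire at Day 28 or the early termination visit, which withdrawn patients are asked to attend.

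Finally, patients are grouped by their current dosage, not randomised, and the groups are filled to equal numbers (3.1, 5.2). A pooled proportion is an average with quota weights, not an estimate for the treated population at large. This also stands.

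**Conclusion.** The point holds as a minor, cheap improvement to a secondary endpoint. The acceptability objective and endpoint are not split by dosage group, and no all-patient estimate or test is planned. Under the assumed alpha, full response and equal preference of 0.70 to 0.75, adding one raises power from 30–46% for a single group's test, or 51–71% for at least one of the two, to 59–80%. The gain depends on broadly similar preference in the two groups; where one group has much weaker preference, the pooled test does worse than the group tests.

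The documents do not support going further and demoting the group tests in favour of the pooled one. That is a trade-off that depends on how far preference varies with dosage, which is unknown. The unstated alpha and test form are missing detail and can matter at borderline counts; they do not make the plan wrong.

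**What to change.** In section 9.4.1.4 and the matching synopsis text, keep the by-group tables and tests and add a prespecified analysis of Question 4 in all treated patients who answered it:
- the proportion preferring DR, with a 95% Clopper-Pearson interval;
- the matching exact one-sided binomial test against 0.5 at 0.025;
- each dosage group's proportion and its own 95% Clopper-Pearson interval beside the pooled figure;
- the number of treated patients with no answer to Question 4.

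The cost is wording only: no extra patients, visits or data. The price in interpretation is that the pooled figure averages over two non-randomised groups and can hide a difference between them, so it should not be reported without the group estimates.

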#### **9.4.2 Interim Analyses**

No interim analysis is planned.

#### **9.5 Criteria for Evaluability of Patient Data**

All patients who received at least one dose of study product will be eligible for evaluation of safety.

### **10 DATA MANAGEMENT CONSIDERATIONS**

#### **10.1 Data Management**

The sponsor's Clinical Data Management group will be responsible for the processing, coding, and validating/cleaning of clinical study data. Patient data will be entered by the investigator or designee using the electronic Case Report Forms (eCRFs) provided by the sponsor. Clinical data will be entered and stored into a validated database. The eCRFs will be provided in the Electronic Data Capture (EDC) system hosted by the sponsor. Trained users will access the system via a secured gateway. Users will be only authorized to access data for their study site. Data will be entered directly into the system from the source documents in lieu of the paper CRFs. On-line and off-line edit checks will be used to prompt the user to provide clean and accurate data. Clinical Data Management will code and monitor the data for accuracy. The data will be coded using the current versions of the MedDRA (Medical Dictionary for Regulatory Activities) and WHODD (World Health Organization Drug Dictionary) dictionaries. An electronic signature will be required of the investigator on the eCRFs, and the study monitor will verify the eCRFs on-line.

Clinical data management activities will be performed by the sponsor in accordance with applicable standards and data cleaning procedures of the sponsor. An audit trail of all data processing will be stored in the database. The study biostatistician will be notified when all subject data are ready for analysis.

Integrity of the database will be assured by limiting access through username/password combination and account control. Authorized access to the database will be provided to those individuals with an inspection/auditing function (Regulatory Authorities/Quality Assurance); "read only" access will be provided to avoid unintentional corruption of the database.

The database will be backed up daily.

## **10.2 Case Report Forms**

Electronic CRFs may be generated and/or printed at any time using the sponsor's EDC system. These eCRFs may be used for electronic submission data archiving or data review. A copy of the final patient-specific eCRFs will be sent to the clinical study sites after database freeze.

## **11 MONITORING, AUDITS, AND INSPECTIONS**

### **11.1 Source Documents**

The investigator or delegate will maintain adequately detailed source documents supporting significant source data for each patient. Source data are defined as all information in original records and/or certified copies of original records of clinical findings, observations, or other activities in a clinical study that are necessary for the reconstruction and evaluation of the study: e.g., medical history, physical examination, laboratory results, and x-ray or ultrasound results. The investigator will also retain all printouts/reports of tests or procedures performed as a requirement of the study. All source data that is printed on thermal paper, including laboratory printouts and ECGs scans, must be photocopied, initialed, and dated as authentic equivalents to the thermal paper documents to enable extended retention time.

The source documents must be available at the time of an audit; a site visit from the sponsor, sponsor representatives, or IRB/IEC; and a regulatory authority inspection.

### **11.2 Monitoring**

Monitoring of the investigational sites will be conducted by the sponsor or contracted to a qualified CRO. The sponsor will determine the extent, nature, and frequency of on-site visits that are needed to ensure that the study is being conducted in accordance with the approved protocol (and any amendments), GCP, and all applicable regulatory requirements. At site visits, the monitor will, as required, assess the progress of the study; check that the study data chosen for verification are authentic, accurate, and complete; verify that the safety and rights of patients are being protected; compare original documents with data entered into the study database; and identify any issues and address their resolution.

The investigator agrees to allow the monitor(s) direct access to all relevant documents, and to allocate his/her time and the time of staff to discuss findings, corrective actions and any relevant issues. In addition to contacts during the study, the monitor may also contact the site prior to the start of the study to discuss the protocol and data collection procedures with site personnel.

### **11.3 Audits and Inspections**

In accordance with the principles of ICH E6 Guideline for Good Clinical Practice, the study site may be inspected by regulatory authorities and/or audited by ApoPharma Quality Assurance (QA) or their designates. The investigator and relevant clinical support staff will be required to be actively involved in audits and inspections, including staff interviews, and to make all necessary documentation and data available upon request.

During the course of the study and/or after it has been completed, one or more investigator site audits may be undertaken by auditors from ApoPharma QA or delegates. The purpose of these audits is to determine whether or not the study is being/has been conducted and monitored in compliance with recognized ICH E6 Guideline for Good Clinical Practice, protocol and approved amendment requirements, applicable local SOPs, and local laws and regulations. It is the responsibility of the investigator and site staff to promptly address, by coordinating with ApoPharma Clinical Research, any deficiencies stemming out of regulatory inspections and ApoPharma QA or delegate audits, and to ensure that agreed-upon corrective and preventive actions are implemented as soon as possible.

An inspection by any regulatory authority may occur at any time during or after completion of the study. If an investigator is contacted by a regulatory authority for the purpose of conducting an inspection or to discuss any compliance issues, he/she is required to contact ApoPharma Clinical Research immediately.

### **11.4 Site Closure**

Upon completion of the study, the investigator must conduct the following activities, when applicable:

- Return all study data and equipment to the sponsor
- Complete data clarifications and/or resolutions
- Ensure that drug accountability is completed and that unused medication is either destroyed or returned to the sponsor, as instructed
- Review site study records for completeness

The sponsor reserves the right to temporarily suspend or prematurely discontinue this study at any time and for any reason. If such action is taken, the sponsor will discuss this with the investigator (including the reasons for taking such action) at that time. The sponsor will promptly inform all other investigators conducting the study if the study is suspended or terminated for safety reasons, and will also inform the regulatory authorities of the suspension or termination of the study and the reason(s) for the action. If required by

applicable regulations, the investigator must inform the IRB/IEC promptly and provide the reason for the suspension or termination.

If the study is prematurely discontinued, all study data must be returned to the sponsor. In addition, the site must conduct final disposition of all unused study medication in accordance with the study procedures.

Financial compensation to investigators and/or institutions will be in accordance with the agreement established between the investigator and the sponsor.

### **11.5 Retention of Records**

In accordance with applicable regulatory requirements, following closure of the study, the investigator will maintain a copy of all site study records in a safe and secure location. The sponsor will inform the investigator of the time period for retaining these records to comply with all applicable regulatory requirements.

## **12 ETHICAL CONSIDERATIONS**

### **12.1 Informed Consent**

Prior to entering a patient into the study, the investigator or a designate must obtain written informed consent from the patient and/or where applicable the patient's legally authorized representative, according to the sponsor's procedures and as described in the Declaration of Helsinki, the Federal Food, Drug and Cosmetic Act, and U.S. applicable Code of Federal Regulations Title 21, Part 50. The investigator will ensure that the patient and/or legal representative is given full and adequate verbal and written information about the nature, purpose, and possible risks and benefits of the study, and is given ample opportunity to ask questions and to discuss the study with family members. The investigator must make a conscientious effort to be fully satisfied that the patient and/or legal representative has truly understood that for which the consent has been given. The patient and/or the legal representative must be notified that he/she is free to discontinue participation in the study at any time, and that such withdrawal will not affect present or future care. In the case of a minor or an incapacitated adult who is capable of forming an opinion and assessing the study information, the investigator must ensure that this individual's decision to not participate or to withdraw from the study will be respected even if consent is given by the legal representative.

The sponsor will provide a model version of the informed consent form to the sites as a separate document. Each site may then revise this version according to the requirements of its individual IRB/IEC.

The patient and/or legal representative will sign and date the consent form prior to the first study intervention, and will be provided with a copy of the signed and dated ICF. Should a

protocol amendment be made, the ICF may need to be revised to reflect the changes to the protocol. The investigator must then ensure that the revised ICF is signed by all patients currently enrolled as well as those subsequently entered in the study.

## **12.2 Institutional Review Board/Independent Ethics Committee**

It is the investigator's responsibility to ensure that the protocol is reviewed and approved by a properly constituted IRB or IEC (according to ICH GCP guidelines, Section 3.2). The IRB/IEC must also review and approve the site's ICF and any other written information that will be provided to patients, prior to any enrollment and the release of any advertisements for patient recruitment. Prior to the start of the study, the investigator or designee must forward copies of the IRB/IEC approval and the approved ICF materials to the sponsor.

If it is necessary to amend either the protocol or the ICF during the study, the investigator will be responsible for ensuring that the IRB/IEC reviews these amended documents, and that IRB/IEC approval of the amended ICF is obtained before any additional patients are enrolled. Copies of the amended ICF and of the IRB/IEC's approval of it must be forwarded to the sponsor as soon as they are available.

